5.1 Inclusion Criteria

Participants are eligible to be included in the study only if all of the following criteria apply:

1. Pre-menopausal females* of age 18 to 49 years old (inclusive) at the time of signing Informed Consent (V1).
2. Surgically (laparoscopy or laparotomy) diagnosed with endometriosis within the last 4 months to 10 years prior to Screening Visit (V1), as documented by medical records.
3. Has moderate to severe endometriosis-related pelvic pain in recent menstrual cycle(s) using a cutoff score of ≥ 4 in a numeric rating scale (NRS) and likely meets eligibility criterion # 10 at Randomization Visit CCI.
4. Has had spontaneous (ie, without hormonal therapy), regular, menstrual cycle with a cycle length between 21 to 32 days (inclusive) for the past 1 month before V1. **Note:** Peri-menopausal women have irregular menstrual cycles, and don't meet this inclusion criterion, and should not be included.
5. Is not expected to undergo a planned gynecological surgery or other surgical procedures for treatment of endometriosis during study participation.
6. Has a normal breast examination at V1. In participants of ≥ 40 years mammography or contrast-enhanced breast MRI performed within the last 12 months prior to Screening (V1) without clinically significant abnormal findings.
Note: Participant with Breast Imaging-Reporting and Data System Classification 1 to 3 is eligible for randomization.
7. Agrees not to participate in another interventional study while participating in the present study.
8. Is able and willing (in the opinion of the Investigator) to adhere to all required study procedures, including:
 - a) Study visits schedule,
 - b) Agree to switch from their usual analgesic to ONLY the rescue medication provided by the study and agree to discontinue their hormone treatment for ERP as outlined in Table 2.
 - c) Agree to timely and duly complete eDiary entries,
 - d) To cooperate and comply with the protocol requirements, including, TVUS, ECG, PK, and pharmacodynamic (PD) assessment among others.**Note:** If participant cannot tolerate or withstand a TVUS, a trans-abdominal ultrasound may be considered as an option, as per the Investigator discretion.

- e) Agree to use 2 forms of non-hormonal contraception throughout the study (from V1 thorough CCI).

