5.2 Exclusion Criteria

Participant is excluded from the study if any of the following criteria apply:

Gynecological Medical Conditions

1. Has a surgical history of hysterectomy and/or bilateral oophorectomy.
Note: Participants who have undergone surgical sterilization (eg, bilateral salpingectomy, tubal ligation, or unilateral oophorectomy) are permitted in the study.
2. Has chronic pelvic and/or non-pelvic pain NOT CAUSED by endometriosis that requires chronic analgesic or other chronic therapy (including, but not limited to, pain caused by interstitial cystitis, bladder pain syndrome, irritable bowel syndrome, hysteroscopic sterilization, adenomyosis [as confirmed by previous MRI], vaginismus, chronic pelvic infection, fibromyalgia, chronic headaches, chronic back pain). Participants using or who will be using frequent opioid analgesics, cannabis, or non-opioids analgesics for chronic pain or recurring pain other than that due to ERP should also be excluded.
3. Has a clinically significant gynecologic condition identified in the screening (including, but not limited to, CCI [REDACTED]).
4. Has a history of ERP that was not responsive at all (refractory) to treatment with CHCs, GnRH agonists and antagonists, progestins, or aromatase inhibitors alone or in combination. The participant that required >2 weeks of continuous use of narcotics for treatment of ERP within 6 months of V1 should also be excluded.
Note: Participants who achieved a partial response or were treatment failures due to side effects should not be excluded.
5. Had undiagnosed (unexplained), abnormal, vaginal bleeding not associated with the baseline condition (endometriosis) within the past 6 months before screening.
Note: Participants may be rescreened after completing treatment for simple ovarian cysts.
6. Has an active sexually transmitted infection (STI) (eg, gonorrhea, chlamydia, or trichomonas) is exclusionary.
Note: Participants may be rescreened after completing treatment for infection.
7. Has no documented normal Papanicolaou (PAP) test within the timeline of current standard of care guidelines or has a significantly abnormal PAP test at Screening (V1) (ie, low-grade squamous intraepithelial lesion, high-grade squamous intraepithelial lesion, atypical glandular cells [any type], squamous cell carcinoma, or adenocarcinoma [in situ or invasive]). The presence of high-risk human papillomavirus (HPV), regardless of PAP result, is exclusionary (e.g. atypical squamous cells).

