Appendix 5 Contraceptive and Barrier Guidance and Collection of Pregnancy Information

Definitions

Woman of Childbearing Potential (WOCBP)

A woman is considered fertile following menarche and until becoming post-menopausal unless permanently sterile (see below).

Women in the following categories are not considered WOCBP

1. Premenarchal
2. Pre-menopausal female with 1 of the following:
 - a) Documented hysterectomy.
 - b) Documented bilateral salpingectomy.
 - c) Documented bilateral oophorectomy.

NOTE: Documentation can come from the study site personnel's: review of the participant's medical records, medical examination, or medical history interview.

3. Post-menopausal female:
 - a) A post-menopausal state is defined as no menses for 12 months without an alternative medical cause. A high FSH level in the post-menopausal range may be used to confirm a post-menopausal state in women not using hormonal contraception or hormonal replacement therapy (HRT). However, in the absence of 12 months of amenorrhea, a single FSH measurement is insufficient.
 - b) Females on HRT and whose menopausal status is in doubt will be required to use 1 of the non-estrogen hormonal effective contraception methods if they wish to continue their HRT during the study. Otherwise, they must discontinue HRT to allow confirmation of post-menopausal status before study enrolment.

Contraception Guidance

Female participants

Female participants of childbearing potential are eligible to participate if they agree to use adequate non-hormonal contraceptive methods consistently and correctly as described in the table below from signing of consent through 30 days from the last dose of study treatment

NOTE: Please consider use of intrauterine devices are prohibited from start of the Screening Period until EOS.

Adequate non-hormonal Contraceptive Methods

Note: Participant should use an acceptable effective method for contraception as specified in the Inclusion Criterion #8

Adequate non-hormonal Contraceptive Methods That Are User Dependent^a Failure rate of <1% per year when used consistently and correctly.

 • Participant has undergone surgical sterilization, or • Bilateral tubal occlusion.

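### The Note to Exclusion Criterion 1 lists unilateral oophorectomy as surgical sterilization, so a site could credit a fertile participant with a contraceptive form she does not have (minor wording error)

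*Protocol*

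**What the plan says.** Four parts of the protocol bear on this point.

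- **Section 5.2, Exclusion Criterion 1.** The exclusion is "Has a surgical history of hysterectomy and/or bilateral oophorectomy". Its Note then says who is not excluded: "Participants who have undergone surgical sterilization (eg, bilateral salpingectomy, tubal ligation, or unilateral oophorectomy) are permitted in the study".
- **Appendix 5, definitions.** The default rule is "A woman is considered fertile following menarche and until becoming post-menopausal unless permanently sterile (see below"). For pre-menopausal women the list that follows has three operations: hysterectomy, "Documented bilateral salpingectomy" and "Documented bilateral oophorectomy". Removal of one ovary is not on it.
- **Appendix 5, table of adequate non-hormonal methods.** Under a heading that gives failure below 1% per year, the first entry is "Participant has undergone surgical sterilization, or", followed by "Bilateral tubal occlusion" as a separate entry. Surgical sterilization is not defined there. A note above the table sends the reader back to Inclusion Criterion 8.
- **Section 5.1, Inclusion Criteria 4 and 8e.** Criterion 4 requires natural, regular cycles of 21 to 32 days in the month before Visit 1. Criterion 8e requires agreement to two non-hormonal forms of contraception for the whole study. Its Note obliges women of childbearing potential to use adequate methods and points to Appendix 5 for which ones.

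**The concern.** A woman with one ovary who cycles regularly can conceive. The Note is right to admit her but names her operation as a sterilization.

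The label matters because the same term does work elsewhere. Appendix 5 accepts surgical sterilization as a contraceptive method in its own right, sets it apart from tubal occlusion, and leaves it undefined. A site that looks through the protocol for its meaning will find examples only in the Exclusion Criterion 1 Note, and one of the three is unilateral oophorectomy.

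What is at stake is pregnancy prevention, not inference. Section 2.3.1 says that effects on fertility, early embryonic development and pre- and post-natal development have not been studied. It gives this as the reason for the precautions against pregnancy. The same section reports no effect in embryo-fetal studies in rats and monkeys, so the risk is incompletely known rather than demonstrated. Hormonal methods and intrauterine devices are prohibited, which leaves few methods to choose from and makes a wrongly counted one matter more.

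**Working it through.** The plan states no figure to reproduce. The check sets the Note's three examples against Appendix 5.

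| Example in the Note | On the Appendix 5 list that ends childbearing potential? | Separately listed as a method with failure below 1% per year? |
|---|---|---|
| Bilateral salpingectomy | Yes | Not needed |
| Tubal ligation | No | Yes, as bilateral tubal occlusion |
| Unilateral oophorectomy | No | No; only through the undefined term surgical sterilization |

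Step 1, status. Appendix 5 removes childbearing potential for loss of both ovaries, not one. Inclusion Criterion 4 requires the woman to be cycling without hormones. An enrolled woman with one ovary and no other listed operation is therefore of childbearing potential.

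Step 2, method. The adequate-methods table is written for women of childbearing potential. If the Note's example is carried into its surgical sterilization entry, such a woman is credited with an adequate method. Nothing in Appendix 5 says that the entry excludes unilateral oophorectomy.

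Step 3, size. Inclusion Criterion 8e requires 2 forms. If the oophorectomy is counted as one of them, the real forms are 2 − 1 = 1. If that one form is a male condom, Appendix 5 accepts it only when combined with another barrier method, so a condom alone would fall short of Appendix 5 as well.

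Step 4, number affected. The documents do not say how many participants have had one ovary removed. No count of women or pregnancies is estimated.

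**The case against.** The best case for leaving the text alone is that the Note concerns eligibility only. It says who is not excluded, sets no contraceptive rule, and is not cited by Appendix 5 or Inclusion Criterion 8e. The duty to use contraception follows childbearing potential, which Appendix 5 defines correctly. An investigator in an endometriosis trial would have to treat a regularly cycling woman as sterile and carry an eligibility example into another section. Pregnancy tests throughout the study, home kits for a delayed cycle, and withdrawal on pregnancy limit exposure further.

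Much of this stands, and it is why the point is minor. It does not remove the error. The list of women without childbearing potential does not block the misreading, because the method table applies to women who do have it. A site can classify the woman correctly and still credit her with the surgical sterilization entry. Pregnancy tests detect a pregnancy; they do not prevent one.

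A reader might go further and infer that the protocol leaves open whether two forms or one method is required, because Appendix 5 lists single methods and Section 2.3.1 accepts a permanent method. The documents do not support that. Appendix 5 refers back to Inclusion Criterion 8, and Section 5.1 makes every inclusion criterion a condition of entry. A coherent reading is that Criterion 8e sets the number of forms and Appendix 5 the acceptable methods. Section 2.3.1 is background risk text that itself defers to Appendix 5 for detail.

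**Conclusion.** The Note mislabels unilateral oophorectomy, and the label conflicts with Appendix 5. That part is certain on the text. The consequence is conditional: if a site carries the label into Appendix 5, and if Inclusion Criterion 8e is otherwise followed, a participant has one real contraceptive form instead of two.

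A reader might infer that some participants would have no contraception at all. That would require Criterion 8e to be set aside as well, and nothing in the protocol permits it. Nor do the documents suggest that women with one ovary should be kept out; the exclusion is for loss of both.

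Sample size, power, the estimand and the primary analysis are untouched. The point is minor: a drafting error in text meant to protect participants, with a bounded consequence and an inexpensive correction.

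**What to change.** 1. In the Exclusion Criterion 1 Note, take unilateral oophorectomy out of the sterilization examples and permit it in its own clause. State there that these women remain of childbearing potential and must meet Inclusion Criterion 8e and Appendix 5.
2. In Appendix 5, define surgical sterilization as bilateral salpingectomy or bilateral tubal ligation or occlusion.

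The first change removes the source of the error. The second stops the undefined term from being filled in from elsewhere; it overlaps with existing entries but costs only a line.

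The cost is two wording changes and a site memo. As a protocol amendment it needs IRB/IEC approval and, where applicable, regulatory approval (Appendix 2). No eligible woman is excluded. If enrolment has closed, the change has less value in this trial, but a memo for participants still on treatment and a correction in any later protocol that reuses the text remain worthwhile.

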- k. Participant compliance with eDiary entries must be CCI during both the SC and the BC to be randomized (information to be provided by the eDiary portal).
- l. CCI
- m. ECG will be performed pre-witness dose and 1.5 hours after dose (witness dose), following the PK Sparse assessment.
- n. CCI
- o. If indicated, participants will be tested for gonorrhea and chlamydia unless they were screened within the past 3 months and have no new sexual partner. Testing for trichomonas and bacterial vaginosis will only be required if abnormal vaginal discharge is present. Testing will be performed locally and may be repeated during the study as needed.
- p. If local regulations indicate that UPT should be performed more frequently, follow local regulations where applicable.
- q. In addition to visits specified, serum pregnancy test also required any time pregnancy is suspected or if UPT is positive (unless pregnancy already confirmed by ultrasound).

CCI

- u. OG-6219 and active metabolite FOR-1011; blood samples for PK analysis will be collected at all visits during the dosing period including the EOT Visit and discontinuation. In addition, for the optional intensive PK sampling, a minimum of C participants per treatment group (incl. Placebo group) will be enrolled on CCI, for entire duration of the study. A complete schedule of PK assessment times is found in Table 8. The witness dose should be administered at site for CCI.

- v. **C** sample collection to be collected within 12±4 hours of last dose of study medication. If not possible, the PK sample should be collected at **C** irrespective of the timing of the last study dose taken.

CCI

- y. Based on determination of positive C-SSRS results for suicidality, the participants will be discontinued from the study medication and referred to a specialist at the Investigator's discretion for further evaluation. In addition, the positive results from C-SSRS evaluation will have to be treated as an SAE and reported to the Sponsor in a timely manner.

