OG-6219 and FOR-1011 displayed inhibition of the hERG channel potassium current with half maximal inhibitory concentration (IC₅₀) values of CCI, respectively, indicating a potential risk of QTc prolongation. Both compounds are however highly bound to plasma proteins, resulting in low free concentrations in vivo and no cardiovascular toxicity or effects on ECG were observed in the in vivo cardiovascular safety study in cynomolgus monkeys. No clinically significant ECG changes were observed in Phase 1 with intense monitoring. To manage the risk of a proarrhythmic activity, in the Phase 2a/b study, ECG recordings at Screening aim to identify and exclude participants with clinically significant cardiac abnormalities. The International Council for Harmonisation of Technical Requirements for Pharmaceuticals for Human Use (ICH) E14 Clinical Evaluation of QT/QTc Interval prolongation and proarrhythmic potential and non-antiarrhythmic drug recommends that ECG recordings be performed at time points of expected C_{max}. Therefore, ECG recordings and vital sign measurements will be performed at CCI

CCI [REDACTED] at each subsequent visit until the End of Study (EOS).

CCI [REDACTED]

[REDACTED] The ultraviolet (UV) absorbance of OG-6219 has a local maximum close to the low end of the natural sunlight wavelength range resulting in molar extinction coefficients values higher than the limit value of 1000 at wavelengths in the UVB spectrum below 305 nm. The penetration of UVB light into human skin is mainly limited to the epidermis and the clinical relevance of photochemical activation by UVB is therefore considered less important than activation by UVA for systemic drugs. The molecular structure of OG-6219 has been evaluated in silico with no alerts for photo-induced genotoxicity, chromosome damage, or photomutagenicity. In addition, no relevant distribution of OG-6219 to the skin or eyes was observed in a pre-clinical study in albino animals. Although, the binding affinity of OG-6219 to melanin has not been evaluated, the risk for phototoxicity of OG-6219 is considered minimal based on the totality of the available data and no specific precautions are therefore warranted.

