2.3.3 Overall Benefit Risk Conclusion

Current medical treatments for ERP provide similar, suboptimal pain control and have safety and tolerability issues that limit their use, often leading patients to have repeated surgical interventions. Thus, there is a need for development of new ERP medical therapies. A local inhibition of estrogen production at the ectopic implants level, for treatment of ERP, such as OG-6219, an oral, potent, selective inhibitor of HSD17 β 1 which can avoid the systemic adverse impact of hormonal treatments.

OG-6219 is a novel HSD17 β 1 enzyme inhibitor being developed for the treatment of moderate to severe ERP. The pharmacological action of OG-6219 is based on its potent and selective binding to HSD17 β 1 and ability to locally inhibit E2 production. The Phase 2a/b PoC and dose-range study aims to assess the efficacy, safety, and tolerability of 3 dose levels of OG-6219 on ERP (CCI BID). Phase 1 data demonstrated pharmacologically relevant endometrial exposure in healthy pre-menopausal participants at 2 higher doses tested (CCI BID and CCI BID). The lower doses of CCI BID are planned based on Phase 1 PK modeling data. CCI

OG-6219 was found to be safe and well-tolerated in Phase 1 with exposure of a total of 71 participants, of which 37 participants were pre-menopausal; 10 pre-menopausal participants were treated with the highest dose of 150 mg BID for 14 days during the first half of the menstrual cycle. No serious or severe AEs were reported. CCI

CCI [REDACTED]
[REDACTED]
[REDACTED]
[REDACTED] In the Phase 2a/b study, participants will be randomized to be treated with 3 dose levels of OG-6219 (CCI [REDACTED] BID), or Placebo for approximately CCI [REDACTED] (up to C cycles, not longer than CCI [REDACTED] of study treatment exposure).

Most relevant pre-clinical findings that may be indicative of safety risks include hERG channel inhibition in vitro CCI [REDACTED] concentrations of both parent (OG-6219) and primary metabolite (FOR-1011), however, both OG-6219 and FOR-1011 are highly bound to plasma proteins resulting in low free concentrations in vivo and no pre-clinical nor Phase 1 evidence of QC prolongation has been found. CCI [REDACTED]
[REDACTED]

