[REDACTED] An increase in liver weight in both rats and cynomolgus monkeys likely attributable to CYP3A4 induction; however, no pre-clinical or Phase 1 data suggest any potential liver toxicity. In addition, no data on fertility and early embryonic development are available. CCI [REDACTED]
[REDACTED]
[REDACTED]

Therefore, in this current Phase 2a/b study, comprehensive panels assessing hematology, clinical chemistry, urinalysis parameters (CCI [REDACTED]), will be closely monitored. Refer to Section 8.4.6 for details of AESIs.

OG-6219 and its primary metabolite FOR-1011 are both metabolized mainly by CYP3A4 and were found to induce CYP3A4 in vitro. No clinical drug interaction studies were conducted to date. However, concomitant administration of OG-6219 with sensitive P-gp and BCRP substrates should be avoided (see Appendix 7).

To manage these risks, necessary precautions to prevent pregnancy will be taken in this study, including pregnancy tests prior to and during the study, and acceptable effective methods of contraception are required for participation. The effect of OG-6219 on systemic hormones, as well as general safety, including ECG and bone effects, will be closely monitored, including blood draws at different points during the first treatment cycle visit and each site visit at the start of next C treatment cycles, as well as during safety follow-up. Cycle length will be monitored by C self-reported bleeding pattern in an eDiary. The ECG measurements will be performed at relevant exposure time points, including T_{max} on Day 1 at the Randomization Visit and after achieving steady state (visit at CC [REDACTED] of the first menstrual cycle after randomization). CCI [REDACTED]
[REDACTED]

[REDACTED] Suicidality will be monitored throughout the study employing a validated questionnaire C-SSRS. Based on

determination of positive C-SSRS results for suicidality, the participants will be discontinued from the study medication and referred to a specialist at the Investigator's discretion for further evaluation. In addition, the positive results from C-SSRS evaluation will have to be treated as an SAE and reported to the Sponsor in a timely manner. Concomitant medications that are sensitive substrates, as well as moderate or strong inhibitors or inducers of CYP3A4 are prohibited. Concomitant medications that are sensitive substrates of P-gp or BCRP should be administered at least 4 hours apart from administration of OG-6219.

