8. Intends to become pregnant during study participation or has a known or suspected pregnancy or has a positive β -hCG or urine pregnancy test at any time before randomization.

Note: If the urine test cannot be confirmed as negative, a serum pregnancy test is required. In such cases, the participant must be excluded from participation if the serum pregnancy result is positive.

9. Has a history of malignancy (except basal cell or squamous cell skin cancer) before signing informed consent.

Note: Any history of hormonal sensitive malignancy (e.g., breast or ovarian cancers) excludes the participant

Other Medical Conditions:

CCI

12. Has an allergy/sensitivity/intolerance to rescue medication provided by Sponsor or any contraindication to its use and in the setting of coronary artery bypass grafting surgery, or has experienced asthma, urticaria, or allergic-type reactions after taking aspirin or other NSAIDs,
13. Has a history or current evidence of any unstable medical condition (including cardiovascular, bone, musculoskeletal, thyroid, diabetes), or other circumstance that in the opinion of the Investigator might confound the results of the study, affect participant's safety or well-being, or interfere with the participant's participation for the full duration of the study.
14. Has a known human immunodeficiency virus infection, and/or an acute or active, recurrent/relapsing, or chronic infection (eg, hepatitis A, B, or C virus).
15. Has a gastrointestinal, liver, kidney, or other disorder that would significantly interfere with the absorption, distribution, metabolism, or excretion of drugs in the opinion of the Investigator.
16. Has a clinically significant abnormal ECG or QT interval prolongation at Screening Visit (V1) or Randomization Visit CCI. Any participant with the following conditions must be excluded:
- a) A marked baseline prolongation of QT/QTc interval (eg, repeated demonstration of a QTc interval CCI milliseconds)
 - b) A history of additional risk factors for Torsade de Pointes (eg, heart failure, hypokalemia, family history of Long QT Syndrome)
 - c) Use of concomitant medications that prolong the QT/QTc interval (such as but not limited to: ibutilide, quinidine, imipramine, erythromycin, and droperidol).

17. Plans to schedule elective surgery during the study execution or had surgery in the past 4 months before screening that continues to require pain management.
18. Suspected active Coronavirus Disease 2019 (COVID-19) infection

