6.8.2 Prohibited Medications and Other Products

The following concomitant medications, therapies, and products are prohibited during study participation (refer to [Table 2](#), [Appendix 6](#), and [Appendix 7](#)). Please note these additional clarifications for prohibited medications/products:

- Sensitive substrates, moderate, and strong inhibitors, or inducers of CYP3A4 ([Appendix 7](#)).
- Sensitive substrates of P-gp and BCRP
Note: For the P-gp and BCRP substrates: they should be administered at least 4 hours apart from OG-6219 ([Appendix 7](#)).
- Endometriosis treatments for symptom relief except rescue medication allowed by protocol ([Appendix 6](#)).
Note: Participants can NOT use local anesthetic (eg, lidocaine patches) NOR receive acupuncture while participating in the study
- The use of analgesic medication different than the rescue medication is prohibited (this is referred as prohibited pain medication, see [Appendix 8](#)).

CCI

- Surgical treatment of endometriosis and use of intrauterine devices are prohibited from start of the Screening Period until EOS.

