Appendix 7 Prohibited CYP3A4 Substrates, Inducers, and Inhibitors; and P-gp and BCRP Substrates

The following medications are prohibited at any time during this study.

Note: The list is intended to be a guidance and may not include all medications in the respective categories.

CYP3A4 Substrates (Sensitive)	Alfentanil, apixabane, alprazolam, aprepitant, atorvastatin, budesonide, buspirone, colchicine, conivaptan, cyclosporine, darifenacin, darunavir, dronedarone, ebastine, eletriptan, eliglustat, eplerenone, everolimus, felodipine, indinavir, lomitapide, lovastatin, lurasidone, maraviroc, midazolam, naloxegol, nisoldipine, pimozide, quinidine, quetiapine, rifabutin, rilpivirine, rivaroxaban, saquinavir, simvastatin, sirolimus, tacrolimus, ticagrelor, tipranavir, tolvaptan, triazolam, and voclosporine.
CYP3A4 Inducers (Moderate and Strong)	Amprenavir, armodafinil, avasimibe, bosentan, carbamazepine, echinacea, efavirenz, etravirine, modafinil, nafcillin, nevirapine, phenobarbital, phenytoin, primidone, rifampin, and rufinamide.
CYP3A4 Inhibitors (Moderate and Strong)	Amiodarone, amlodipine, atazanavir, boceprevir, bicalutamide, chlorzoxazone, cimetidine, cilostazol, ciprofloxacin, clarithromycin, clotrimazole, cobicistat, cyclosporine, danoprevir, diltiazem, erythromycin, fluconazole, fluvoxamine, fosamprenavir, fluoxetine, ginkgo, goldenseal, grapefruit juice, isoniazid, istradefylline, itraconazole, ivacaftor, ketoconazole, lopinavir, mibefradil, nefazodone, nelfinavir, nicardipine, paritaprevir, posaconazole, products containing Seville oranges, ranitidine, ranolazine, rifabutin, ritonavir, telaprevir, telithromycin, tiranavir, tofisopam, troleandomycin, verapamil, voriconazole, and zileuton.
Sensitive substrates for P-Glycoprotein (P-gp)	Digoxin, dabigatran etexilate, edoxaban, fexofenadine, loperamide, morphine Note: should be administered at least 4 hours apart from OG-6219
Sensitive substrates for Breast Cancer Resistance Protein (BCRP)	Rosuvastatin, sulfasalazine, methotrexate, prazosin, glyburide, teriflunomide, cladribine Note: should be administered at least 4 hours apart from OG-6219

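### QT-prolonging co-medication is barred as a class at entry, but no visible rule keeps that class barred during dosing: a small safety gap that is cheap to close

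*Protocol*

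**What the plan says.** Criterion 16 in Protocol section 5.2 deals with QT risk at entry. Its part c excludes for "Use of concomitant medications that prolong the QT/QTc interval (such as but not limited to: ibutilide, quinidine, imipramine, erythromycin, and droperidol"). The lead sentence of the criterion ties it to the Screening and Randomization visits.

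The on-study rules are in section 6.8.2, which points to Table 2 and Appendices 6, 7 and 8. The drug-interaction class named there is "Sensitive substrates, moderate, and strong inhibitors, or inducers of CYP3A4", followed by P-gp and BCRP substrates. Appendix 7 opens with "The following medications are prohibited at any time during this study" and lists drugs under CYP3A4, P-gp and BCRP headings only.

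On the risk itself, section 2.3.1 reports hERG inhibition by parent and metabolite, "indicating a potential risk of QTc prolongation". Its stated response begins "To manage the risk of a proarrhythmic activity, in the Phase 2a/b study, ECG recordings at Screening aim to identify and exclude participants"; that exclusion is aimed at relevant cardiac findings, and ECGs on study follow. Section 2.3.3 adds the reassurance that "no pre-clinical nor Phase 1 evidence of QC prolongation has been found" (QC evidently means QTc). The co-medication control it states is "Concomitant medications that are sensitive substrates, as well as moderate or strong inhibitors or inducers of CYP3A4 are prohibited", together with a spacing rule for P-gp and BCRP substrates.

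**The concern.** The reason for excluding users of QT-prolonging drugs is to avoid adding their effect to that of a compound that may itself prolong QTc. That risk starts with the first dose, yet the visible rule for the class is applied before dosing and is not repeated afterwards. A woman could be refused entry for taking imipramine, while another could start imipramine in her second treatment cycle without breaching any visible rule.

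What is at stake is the safety of individual participants. The reassuring human evidence is short: the Phase 1 work described in sections 2.3.1 and 2.3.3 exposed 71 women for up to 14 days, 10 of the pre-menopausal women at the highest dose. This study doses for three menstrual cycles. Efficacy results and comparisons between arms are not at issue.

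**Working it through.** Apart from two simple counts this is a text comparison, and the plan gives no figure to reproduce.

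**1. Is the QT class in any visible on-study rule?**

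- Section 6.8.2: CYP3A4 drugs, P-gp/BCRP substrates, other endometriosis treatments, non-rescue analgesics, endometriosis surgery and intrauterine devices. No QT class and no reference back to criterion 16c.
- Table 2: hormones and contraceptive devices, analgesics, herbal and cannabis products, glucocorticoids. No QT row.
- Appendix 6: rescue medication only. Appendix 8: pain medication only.
- Appendix 7: its note that the list may be incomplete extends it only within its own CYP3A4, P-gp and BCRP categories.
- Criterion 25, on treatments that might interfere with the study, points only to Appendix 7.
- Section 8.1.9.1 directs the medication review to section 6.8.2, not to criterion 16c.

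**2. Look up the five drugs named in 16c.**

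| Drug | Visible on-study bar |
|---|---|
| Quinidine | Yes, Appendix 7 (sensitive CYP3A4 substrate) |
| Erythromycin | Yes, Appendix 7 (CYP3A4 inhibitor) |
| Ibutilide | None |
| Imipramine | None |
| Droperidol | None |

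So 2 of 5 are barred and 3 of 5 are not. The class is open-ended, so this illustrates the gap and does not measure how much of the class is covered.

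**3. Compare with other drugs barred at entry.** CYP3A4 drugs are barred before dosing (criterion 26) and again on study (section 6.8.2, Appendix 7). Table 2 drugs are barred at entry by criterion 31, and the table states that the bar runs throughout the study. Grapefruit and Seville orange products are barred before dosing and until the final dose (section 5.3). For these the continuation is written out; for the QT class it is not.

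**4. Number on active drug.** SAP section 4.3 gives 95 per group and 380 in total. Three active groups: 3 × 95 = 285, and 285/380 = 75%. This is the number who receive the compound, not the number who would also take a QT drug; the documents give no rate for that.

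**5. Could the scheduled ECGs miss it?** I read the ECG row of the Schedule of Activities (section 1.3) against its timing row. ECGs fall at Visit 1, TRC1 start, the later cycle-1 visit, TRC3 start, start of safety follow-up, end of safety follow-up, and discontinuation. There is none at TRC2 start or at Day 14 after stopping, both of which are phone contacts. After the first dosing day, that leaves 3 scheduled ECG visits up to the end of treatment: the cycle-1 visit, TRC3 start and the start of safety follow-up. At TRC1 start, the cycle-1 visit and TRC3 start, footnote m applies: "ECG will be performed pre-witness dose and 1.5 hours after dose (witness dose), following the PK Sparse assessment".

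The interval from the cycle-1 visit to TRC3 start therefore contains the rest of TRC1 and all of TRC2. At the cycle length in section 4.1, TRC2 alone is about 21 to 32 days. A short QT-drug course begun and finished within TRC2 would have no scheduled ECG.

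**The case against.** **Redaction.** Section 6.8.2 has a blacked-out block and Table 2 has blacked-out notes, which are the two places where a QT rule would sit. Its absence cannot be proved, so the sponsor should be asked rather than told. A hidden rule does look unlikely. The block in 6.8.2 directly follows the analgesic item, the visible marker for Table 2's note d is on the cannabis row, and the visible co-medication controls in section 2.3.3 cover only CYP3A4 and P-gp/BCRP.

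**Criterion 16c may be meant to continue.** The visit timing is attached to the ECG finding in the lead sentence, 16c speaks of concomitant medication, and section 6.8 defines that to include drugs received during the study. Criterion 22 shows that section 5.2 can contain on-study conduct rules. The reading is arguable, but criterion 16 is worded as a rule about who must be excluded, and nothing visible makes it operate after randomisation.

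**Screening plus monitoring is a reasoned choice.** The signal is in vitro, protein binding is high, and neither the monkey study nor Phase 1 showed an ECG effect of concern. CYP3A4 drugs are barred for a separate reason, the lack of clinical interaction studies. On study there are triplicate ECGs timed to exposure, a QTcF discontinuation rule that includes a change above 60 ms (section 7.2), medication review at every contact (section 8.1.9.2), and investigator discretion to stop treatment. All of this stands and is why the point is small. But these measures record the drug or detect the prolongation; they do not tell a site or participant not to start the drug.

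**Cost and clarity.** An amendment needs ethics and, where applicable, regulatory approval (Appendix 2), and an open class leaves sites to judge which drugs qualify. Both are fair and bear on how the fix is made.

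**Conclusion.** The concern holds on the visible text, as a minor point. The protocol bars QT-prolonging drugs as a class at entry and does not visibly carry that class through dosing. Coverage on study is partial, through overlap with the CYP3A4 and other lists.

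The gap concerns individual safety among the 285 women (75%) planned to receive active drug. No event count can be given because no rate of new QT-drug use is stated. Sample size, power and the efficacy analysis do not change.

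The conclusion rests on two assumptions: that the redacted text in section 6.8.2 and Table 2 contains no QT rule, and that the Schedule of Activities, whose columns were recovered from a PDF, has been read correctly. Confidence is medium, mainly because of the first.

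**What to change.** Ask the sponsor to confirm whether the redacted text already bars QT-prolonging drugs on study. If it does not, add one line to section 6.8.2 and one to Table 2 prohibiting drugs known to prolong the QT/QTc interval, as in criterion 16c, from randomisation to the last dose of study treatment. Naming the reference list that sites should use would settle which drugs qualify.

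No new data or procedures are needed, since the line would be checked at the medication reviews already planned. The costs are a few more recorded deviations and the approvals that an amendment requires; the lines could travel with another amendment. If dosing has ended, carry them into the next protocol for this compound.
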